Primary objective: In relation to the participants' chronotype, the objective will be to evaluate the effect of irregular working hours on the quality of sleep, on the circadian rhythm of activity levels and on motor control, to identify the type of shift with less impact on the state of health of the hospital staff.

Secondary objective: Evaluations of heart rate variability, circadian rhythm of activity levels, sleep quality and motor control for the definition of alterations related to the effect of the shift.

[figure not shown]
STUDY DESIGN

The project involves the recruitment of nursing staff of the IRCCS Galeazzi Orthopedic Institute of Milan, which is subjected to three types of shift:

- GROUP 1: total duration 5 days, 24-hour shifts;
- GROUP 2: total duration 10 days, 24-hour shifts;
- GROUP 3: diurnal shifts only (control).

The experimental design is schematized as shown in Figure 1.

Figure1: Experimental design.

Upon recruitment, all participants will undergo to the following evaluations (see Figure 2):

- Questionnaire Horne-Ostberg Morningness-Eveningness Questionnaire (MEQ) for the determination of the chronotype (Horne JA, Ostberg O. 1976);
- International Physical Activity Questionnaire (IPAQ) for the assessment of the level of physical activity;
- QRISK2-2017 questionnaire for cardiovascular risk assessment (Hippisley-Cox J, 2010; Hippisley-Cox J, 2008).

All the questionnaires are validated in Italian except the QRISK2-2017, which will be administered by medical personnel.

During the entire duration of the shift, all participants will be subjected to actigraphic monitoring to assess the quality of sleep and circadian rhythm activity-rest. Monitoring will start from the first day of the shift and will continue for 10 consecutive days for all three groups. During the entire duration of the monitoring the participants will have to fill in a diary on which they will note the hours of alarm, of falling asleep and any intervals of time during which the actigraph will be removed.

At the beginning, after 5, 7 and 8 days of shift for GROUP 3, GROUP 2 and GROUP 1, respectively, participants will undergo to:

- Evaluations of the motor control and level of neuromuscular activation of the finger flexor muscles;
- Heart rate variability analysis by monitoring heart rate;
- Profile of Mood States (POMS) questionnaire for the determination of the mood profile.

Figure 2

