The population consists of about 120 potential participants recruited within the nursing staff belonging to the Galeazzi Orthopedic Institute, of which 60 potentially belong to GROUP 1, 20 to GROUP 2 and 40 to GROUP 3.

Inclusion criteria: Both sexes who have a continuity of shift in the specific group of at least one year will be included in the study.

Exclusion criteria: All participants will be excluded from the project with documented presence of cardiovascular, endocrine and metabolic diseases and / or pharmacological therapies in place that can modulate the heart rate and the quality of sleep. Participants with self-declaration of pregnancy status will also be excluded from the study.

Participation and completion of the study: The participant is considered enrolled in the study when providing written informed consent. No study procedure will be initiated before the Informed Consent is signed. Participation in the study may end before its completion for the reasons described in the dedicated section. The whole study ends when the last subject has completed the study or has been withdrawn from the study.

Interruption of the participation to the study: Participants have the possibility to withdraw from the project at any time. In the latter case, personal data will be completely erased while the scientific data collected until the time of the possible withdrawal, will be used anonymously for purely scientific purposes. Participants must promptly notify the inability to continue the study.

The study does not provide for follow-up but some samples or evaluations could be lost. Any participants lost during the study will not be replaced.

CLINICAL EVALUATIONS

Evaluation of the chronotype: the administration of the MEQ questionnaire will allow, on the basis of the scores obtained, dividing the sample into the three corresponding chronotypes (M-Types, N-Types to E-Types). Morningness/eveningness can have a major impact on the well being of the individual through sleep-related influences, as it interferes with normal daily functions.

Assessment of the level of physical activity: the IPAQ questionnaire includes 4 sets of questions that investigate four different aspects of the level of physical activity in relation to health.

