Assessment of the psychological state: the POMS questionnaire identifies and quantifies affective states such as tension, depression, aggression, vigor, fatigue, and confusion. These six aspects prove to be particularly useful for assessing the subject's state of stress, fatigue and energy.

Cardiovascular risk assessment: The extent of cardiovascular risk will be calculated in all participants via QRISK2-2017 questionnaire. The questionnaire requires the inclusion of parameters such as gender, ethnicity, age, weight and height, smoking and relative frequency, the presence of diabetes, hypertension, episodes of angina, fibrillation, rheumatoid arthritis, chronic diseases in the kidney, cholesterol / HDL ratio and systolic blood pressure. The information will then be inserted into a special algorithm (<https://qrisk.org>), which will return the percentage of probability of risk involved in a cardiac problem in the next 10 years.

Evaluation of force and motor control: To evaluate the possible variations of force and motor control, the maximal voluntary isometric force (MVC) of the flexor muscles of the dominant hand fingers and their activation will be evaluated in all participants. Once the MVC has been identified, sub-maximal contractions will be required at 20, 40, 60 and 80% MVC, each lasting 20 seconds. During contraction, in addition to the force signal (model SM-2000 N, Interface, Scottsdale, UK) the surface electromyographic signal (sEMG) will be detected by the flexor muscles of the fingers. The analysis of the force signal will be evaluated (i) the ratio between the standard deviation of the force signal during the plateau phase and the mean of the signal itself (coefficient of variation, CV), as an index of stability of the muscle contraction and (ii) the distance of the force signal with respect to the target (DF) as an index of accuracy. The electromyographic signal will be analyzed in the time and frequency domain: during the maintenance period of the force plateau, the quadratic root mean (root mean square, RMS) and the mean frequency (mean frequency, MF). The temporal trend of the two signals will be used as markers of neuromuscular fatigue.

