Assessment of hearth rate variability (HRV): The study of HRV consists in the measurement and analysis of the heart rate, in order to deduce some important information such as assessing the risk of cardiac and heart attack arrhythmias or the balancing of the activity between the sympathetic and parasympathetic nervous system (sympathovagal balance). The heart rate will be measured at rest for duration of at least ten minutes through a heart rate monitor (Polar mod 810, Polar, Finland), which allows R-R detection of the heart rate. The measurement will be performed with the participants in a supine position and according to the guidelines of the American Heart Association. The recordings will be analyzed in the time and frequency domain using software (Kubios, <http://kubios.uef.fi>). In the time domain the mean quadratic root of the standard deviation of all the intervals between the QRS complexes will be calculated (RMSSD). The size of the RMSSD is an indication of the activation of the Parasympathetic Nervous System. In the frequency domain the powers of the frequencies included between 0.01 and 0.4 Hz will be calculated. In this case, the Low Frequency (LF, between 0.04 and 0.15 Hz) will be calculated, considered a marker of activation of the sympathetic nervous system and the activity of regulation of the baroreceptors; the High Frequency, between 0.15 and 0.4 Hz), considered as an expression of the activity of the parasympathetic nervous system and influenced by the frequency and depth of respiration. The LF/HF ratio is generally used as a balancing index between the sympathetic and parasympathetic nervous system.

Assessment of the sleep quality and the circadian rhythm of physical activity levels: for this evaluation we will use the use of actigraphs. Actigraphy is a method used to evaluate the circadian rhythm of activity levels and sleep parameters. The Actiwatch Software will be used to obtain activity data, expressed in activity counts and recorded for each minute throughout the monitoring period. For each subject, the data will be processed to evaluate the circadian rhythm of activity levels. The software for sleep analysis allows to extrapolate some parameters indicative of the quantity and quality of sleep: (i) Sleep Efficiency (SE), percentage of time spent in bed with actual sleep; (ii) Assumed Sleep (AS), difference between beginning

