A Shapiro-Wilk test will be applied to check the normal distribution of the sample.

A linear mixed ANOVA with Bonferroni correction, with a Tukey-Kramer post-hoc test will be applied to estimate the effects of the work shift on the different chronotypes (quality of sleep, circadian rhythms of activity levels, motor control, cardiovascular risk and mood profile). In the opposite case, the Box and Cox method will be used as non-parametric approaches.

MONITORING, VERIFICATION, STUDY INSPECTION

Study insurance and monitoring: Given the non-invasive nature of the procedures envisaged by the study, monitoring activities and the stipulation of an ad hoc insurance policy are not considered necessary.

Verification and inspection: The main investigator will allow monitoring, verification and inspections related to the study by the Ethics Committee, the promoter, the bodies required by law, the quality assurance commissions of all documents. The main investigator will ensure the possibility of inspections if applicable to the structures connected to the study. Participation as a principal investigator in this study implies acceptance of a possible inspection by the competent authorities and university offices for quality assurance.

ADHERENCE TO ETHICAL, REGULATORY AND ADMINISTRATIVE FACTORS

Ethics Committee: This study will be conducted according to the ethical principles of the Helsinki Declaration and the indications of good clinical practice, in compliance with regulatory requirements and legal obligations. By subscribing this protocol, the experimenters agree to comply with these requirements and to conduct the study diligently and efficiently and in accordance with this protocol.

This protocol and any amendments will be submitted to the EC in accordance with the legal obligations for formal approval of the study. The EC decision on the conduct of the study will be written to the coordinator and a copy of this decision will be provided to the promoter's representative before the start of the study.

Written informed consent is required for all participants.

Information to the participants and their consent: Complete information on the study and details of the protocol must be discussed with each potential subject, and an informed written consent must be obtained for all participants before carrying out any procedure or registration related to the study.

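### The work-shift analysis tests an undefined 'cardiovascular risk'; if this means QRISK2-2017, unadjusted age or sex differences between rosters can be reported as a shift effect

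*Combined protocol and SAP*

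**What the plan says.** The Statistical Analysis section applies a linear mixed ANOVA, with Bonferroni correction and Tukey-Kramer comparisons, to estimate work-shift effects across chronotypes on "quality of sleep, circadian rhythms of activity levels, motor control, cardiovascular risk and mood profile". It names no covariate, and neither does any other section.

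Two measurements could be the cardiovascular item:

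- **QRISK2-2017.** Clinical Evaluations states: "The extent of cardiovascular risk will be calculated in all participants via QRISK2-2017 questionnaire". On its inputs it says: "The questionnaire requires the inclusion of parameters such as gender, ethnicity, age, weight and height", followed by smoking, several diagnoses, cholesterol ratio and systolic pressure. The result is a 10-year percentage. Study Design lists the "QRISK2-2017 questionnaire for cardiovascular risk assessment" under the sentence "Upon recruitment, all participants will undergo to the following evaluations", and schedules no repeat.
- **HRV.** The secondary objective begins "Evaluations of heart rate variability, circadian rhythm of activity levels, sleep quality and motor control". Clinical Evaluations says that HRV informs "assessing the risk of cardiac and heart attack arrhythmias". Study Design places HRV in the battery done at the start and again after some days of shift.

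The groups are the nurses' existing rosters. The inclusion criterion is "Both sexes who have a continuity of shift in the specific group of at least one year". There is no age limit, matching or stratification. The potential group sizes are 60, 20 and 40.

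**The concern.** A reader cannot tell from the plan which variable will be tested. On the QRISK2 reading the problem goes beyond ordinary possible confounding, because age and sex enter the outcome by construction. A roster with older nurses, or more men, will tend to score higher even if the shift does nothing. Bonferroni and Tukey-Kramer deal with multiplicity, and Box-Cox with distribution shape; none of them deals with a difference in composition between rosters. Since the score is taken once, no within-person change is available either, and the comparison is purely cross-sectional.

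The study aims to identify the roster with the least impact on health, and its risk/benefit paragraph says that the results may inform changes to the shift system. A roster labelled as raising cardiovascular risk because its staff are older would mislead that decision.

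**Working it through.** **1. Which variable?** The text points both ways.

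- For QRISK2: it is the only measurement that the protocol calls cardiovascular risk, and it does so in both Study Design and Clinical Evaluations.
- For HRV: the repeated battery in Study Design runs motor control, HRV, mood (POMS). The outcome list ends motor control, cardiovascular risk, mood. A mixed model suits a repeated measure. The other listed outcomes are measured during or across the shift, and the other recruitment questionnaires (MEQ, IPAQ) are not listed as outcomes. HRV is in a stated objective; QRISK2 is in neither.

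On the QRISK2 reading, HRV is a stated objective missing from the outcome list. On the HRV reading, QRISK2 is collected with no stated analysis. Either way the term needs defining.

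**2. How large could the distortion be on the QRISK2 reading?** The plan has no figure of its own here. Its one calculation, 37 participants, is for sleep efficiency and does not bear on this point.

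Inputs from the documents: 60, 20 and 40 potential participants (the full pools, so an upper bound) and alpha 0.05. If Bonferroni covers three pairs, which the plan does not state, alpha is 0.05/3 = 0.0167.

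Assumed, because the documents give none of these:

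- log-risk slope per year of age, a = 0.06 or 0.10;
- age SD, S = 8 or 11 years;
- log-risk slope per mmHg of systolic pressure, b = 0.01 or 0.02, with pressure SD 13 mmHg;
- log-risk SD from other inputs, o = 0, 0.3 or 0.5;
- age gap d = 2, 3 or 5 years.

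Formulas, with no true shift effect:

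- SD of log score = √[(aS)² + (13b)² + o²]
- noncentrality = (a·d/SD) / √(1/n₁ + 1/n₂)
- false-positive rate = two-sided rejection probability of the noncentral t with n₁ + n₂ − 2 degrees of freedom.

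Extremes for Group 1 v 3, where √(1/60 + 1/40) = 0.204, and d = 5:

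- Lowest (a 0.06, S 11, b 0.02, o 0.5): SD = √(0.4356 + 0.0676 + 0.25) = 0.868; shift 0.30/0.868 = 0.346 SD; noncentrality 1.69; rate 0.39.
- Highest (a 0.10, S 8, b 0.01, o 0): SD = √(0.64 + 0.0169) = 0.810; shift 0.50/0.810 = 0.617 SD; noncentrality 3.02; rate 0.85.

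Range over all 24 settings, log scale:

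| Age gap | 1 v 3, alpha 0.05 | 1 v 3, alpha 0.0167 | 2 v 3, alpha 0.05 | 2 v 3, alpha 0.0167 |
|---|---|---|---|---|
| 2 years | 0.10-0.22 | 0.04-0.11 | 0.08-0.14 | 0.03-0.07 |
| 3 years | 0.17-0.43 | 0.08-0.27 | 0.12-0.26 | 0.05-0.14 |
| 5 years | 0.39-0.85 | 0.23-0.72 | 0.24-0.60 | 0.12-0.42 |

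In simulation on the untransformed percentage, Group 1 v 3 at 0.05 is somewhat lower: 0.07-0.19, 0.10-0.37 and 0.25-0.78.

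A separate simulation of the three-group F-test (slope 0.06-0.09, age SD 9, residual SD 0.5, Group 3 older) gave about 0.23 for a 3-year gap and 0.46-0.56 for a 5-year gap. With age in the model it gave 0.05-0.06.

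Sex alone: 40% v 20% men, with an assumed log-risk difference of 0.4-0.7, gives 0.05-0.21 for Group 1 v 3.

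**3. Precision after adjustment.** The 95% CI factor for the adjusted ratio is exp[t(0.975, 115) × √((13b)² + o²) × √(1/n₁ + 1/n₂)], with t = 1.981.

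- 1 v 3: exp(1.981 × 0.130 × 0.204) = 1.05 to exp(1.981 × 0.564 × 0.204) = 1.26.
- 2 v 3, where the last term is 0.274: 1.07 to 1.36.

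**The case against.** The strongest reply is that the item is really HRV. The order of the list, the mixed model and the secondary objective all support this, and on that reading the scoring mechanism and every figure above fall away. This stands as a real alternative. A reader might infer that the plan definitely tests QRISK2 without adjustment; the documents do not settle that. They do not settle on HRV either, so the request to define the term survives on both readings.

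The second reply is that nothing shows the rosters differ in age or sex. That is correct. The rates rest wholly on assumed slopes, SDs and gaps, and a 2-year gap tested at 0.0167 gives only 0.04-0.11 for Group 1 v 3. A reader might infer that a false shift effect is likely; the documents support only that it is possible and unguarded. The return to about 0.05 with age in the model also holds by construction, because age was the only imbalance simulated.

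Third, ethnicity is another fixed input that an age and sex model leaves out. That stands as residual confounding.

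One might also object that it is odd to adjust a score for its own inputs. Here it is reasonable: what remains reflects inputs such as pressure, cholesterol ratio, weight and smoking, which a roster could plausibly change.

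**Conclusion.** The point holds conditionally and is minor. The outcome is undefined between two measured variables. If it is QRISK2, the planned comparison is an unadjusted cross-sectional contrast between existing rosters on a score built partly from age and sex. The size of any bias cannot be known from the documents. With the full pools and the assumed inputs, a small age gap does modest harm and a 5-year gap serious harm; fewer participants would lower these rates.

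A reader might extend this to the main result or to the other listed outcomes. The documents do not support that on this ground: the main outcome is sleep efficiency, which is not computed from age or sex. Whether age confounds the other outcomes is a separate question, not claimed here.

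**What to change.** Add to the Statistical Analysis section, in words such as these:

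> HRV and QRISK2-2017 are separate outcomes. QRISK2 at recruitment is compared across shift groups only in a linear model on the log scale with age and sex as covariates, and is reported as adjusted ratios with 95% confidence intervals. This is a cross-sectional comparison after at least one year on the roster.

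A simpler alternative is to report QRISK2, age and sex by roster descriptively, with no test.

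The cost is two or three sentences. Both covariates are already collected for the score, so no visit, measurement or participant is added. Adjustment does not remove other differences between rosters, and precision for Group 2, with at most 20 nurses, will be low.

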and end of sleep; (iii) Sleep Latency (SL), period of time between bed and sleep; (iv) Movement and Fragmentation Index (MFI), percentage of time spent moving indicative of the fragmentation of sleep and (v) Immobile Time (IT) total time spent without movement, between sleep from start to sleep.

To determine the circadian rhythm in the three chronotypes, the data relating to the activity provided by the actigraph would be analyzed using the single Cosinor method, which identifies and evaluates the cosinusoidal mathematical function that it is better suited to data as a function of time. The function defines three parameters that are characteristic of each rhythm: MESOR (Midline Estimating Statistic of Rhythm), amplitude and acrophase. The rhythmic parameters of the activity levels will be elaborated with the Cosinor Population, in order to evaluate the rhythmic characteristics of the levels of activity for each chronotype.

EVALUATION AND REGISTRATION OF ADVERSE REACTIONS

Safety and evaluation of adverse reactions in relation to the techniques used Participating subjects will be closely monitored for possible side effects.

Criteria for suspension of the study: Suspension from the study is planned based on the doctor's assessment in the cases specified above. Participants will be informed in the consensus session that participation in the study can be interrupted at any time.

Data collection for retired participants: Even if participants can withdraw from the study, undesirable effects will be recorded.

Risk/Benefits Report: As no invasive measures are planned within the study, participants will not be exposed to particular risks. The results will provide useful information to be able to reason on any revaluations of the shift system by making any changes.

STATISTICAL ANALYSIS

The sample size was calculated (Sigmaplot mod software 12.5) on the basis of the results of a previous study (Martin et al., 2015), which is structured with an experimental design similar to that proposed in the present project. In consideration of the main objective of the project, the sleep efficiency was identified as the main outcome. An analysis of variance (ANOVA) model, a minimum detectable change percentage of 5%, a residual standard deviation of 6.9 and a number of groups equal to 3 were considered for sample size quantification. On these basis, a number of 37 participants would guarantee a statistical power > 0.80 with an α value <0.05.

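### Does calling Box-Cox a non-parametric fallback leave the sleep-efficiency analysis without a sound plan for non-normal data?

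*Combined protocol and SAP*

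**What the plan says.** All the relevant analysis text is in the Statistical Analysis section of the combined protocol and SAP. The order of steps is:

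- Normality check: "A Shapiro-Wilk test will be applied to check the normal distribution of the sample". No threshold is given, and model residuals are not mentioned.
- Main model: "A linear mixed ANOVA with Bonferroni correction, with a Tukey-Kramer post-hoc test will be applied to estimate the effects of the work shift", across the chronotypes.
- Fallback: "In the opposite case, the Box and Cox method will be used as non-parametric approaches". Coming after the normality check, the opening words can only sensibly mean that normality has failed.

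The same section states that "the sleep efficiency was identified as the main outcome", and it sizes the study on "a minimum detectable change percentage of 5%, a residual standard deviation of 6.9 and a number of groups equal to 3". Under Clinical Evaluations the outcome is defined as "Sleep Efficiency (SE), percentage of time spent in bed with actual sleep", so planning is on the percentage scale. The expected pool is about 120 nurses, split 60, 20 and 40 across the three shift groups.

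**The concern.** Box-Cox estimates a power by likelihood under a normal model, and a parametric ANOVA of the transformed values follows. Calling this non-parametric is a mistake. A reader could be told that a distribution-free method was used when none was, and could fairly ask which of the two was intended.

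The rule also reaches the main outcome. Sleep efficiency is capped at 100, so left skew is plausible and the fallback may be triggered. The shift effect would then be estimated on a power scale chosen from the data, while the planned 5% change is in the original units. The plan does not say how the power is chosen, whether one power serves all groups and times, how results are back-transformed, or what happens to zeros. Standard Box-Cox needs strictly positive values, and a secondary outcome such as "Sleep Latency (SL), period of time between bed and sleep" might contain zeros.

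If this damaged error rates, power or the ability to read the effect in percentage points, the primary result would be at stake.

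**Working it through.** **1. The plan's own figure.** Inputs from the Statistical Analysis section: difference 5, SD 6.9, 3 groups, α 0.05. For a one-way ANOVA with two means 5 apart and the third midway, the noncentrality is λ = n·d²/(2·SD²), with 2 and 3(n−1) degrees of freedom.
- n = 37 per group: λ = 37 × 25 / (2 × 47.61) = 9.71, power 0.792.
- n = 38 per group: λ = 9.98, power 0.803.
- 37 in total (12.33 per group): λ = 3.24, power 0.32.

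The 37 is reproduced, nearly, as a per-group number on the original scale. That reading is a separate matter. Here it only confirms that the planning effect is 5 units of sleep efficiency against an SD of 6.9.

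**2. How likely is the fallback?** The documents give no mean or shape for sleep efficiency, so shapes must be assumed. Seven capped shapes were tried, all with SD 6.9 and one value per person: 100 minus a gamma variable with mean 75 to 85, and beta with mean 75 to 90. Shapiro-Wilk rejected in 11–81% of samples at n = 37 and 29–100% at n = 120. For normal data it rejected in about 5%. The trigger is plausible but not certain.

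**3. Error rates and power if it is used.** Groups of 60, 20 and 40, gamma shape, SD 6.9. Null: all means 85. Alternative: means spread over 5 points. Three separate simulations gave:

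| Run | Quantity | Untransformed | Box-Cox | Kruskal-Wallis |
|---|---|---|---|---|
| A | Type I error | 0.044 | 0.043 | 0.044 |
| A | Power | 0.889 | 0.934 | 0.917 |
| B | Type I error | 0.053 | 0.053 | 0.053 |
| B | Power | 0.90 | 0.94 | 0.93 |
| C | Type I error | 0.050 | 0.055 | 0.053 |
| C | Power | 0.885 | 0.943 | 0.938 |

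Box-Cox holds its level and does at least as well as the rank test whose absence is the complaint.

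**4. Can the 5-point effect still be read?** With T(x) = (x^p − 1)/p, the raw transformed gap T(90) − T(85) is:
- p = 3.2: 9.37e4
- p = 4.5: 3.14e7
- p = 5.7: 6.72e9

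The powers 3.2 and 5.7 are about the 5th and 95th percentiles of the fitted power for the gamma shape with mean 85 at n = 120. The ratio of the extremes is about 70,000, which looks alarming but only reflects a change of units. Dividing by the usual scale factor 85^(p−1) gives:
- 9.37e4 / 1.757e4 = 5.33
- 3.14e7 / 5.66e6 = 5.54
- 6.72e9 / 1.170e9 = 5.74

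The range is then 5.74 / 5.33 = 1.08-fold.

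The transformation is also monotone and invertible. In an illustration with assumed left-skewed data and raw means 85.0, 85.0 and 80.0 (fitted power about 5.3), the back-transformed centres were 86.1, 86.0 and 81.1. The gaps to the third group are 86.1 − 81.1 = 5.0 and 86.0 − 81.1 = 4.9, against 5.0 raw. Over 1,000 simulated studies at 60/20/40 the mean back-transformed gap was 4.90 points against 4.96 raw. The median absolute difference was 0.16 points and the 95th percentile 0.61. A separate run gave 4.92 against 4.99.

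**5. Sample or residuals?** With a 5-point spread between groups, the two ways of running Shapiro-Wilk rejected in 0.037 and 0.045 of samples. The choice changes almost nothing at the planned effect size.

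**The case for a change.** The strongest opposing case is that the sentence cannot be right under any reading. If Box-Cox was meant, the label is wrong and the reporting rule is absent. If a distribution-free test was meant, the wrong method is named. A contingency rule should be settled before data are seen, and the results are meant to inform a review of the shift system, which needs percentage points.

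The mislabel and the missing detail stand. The transformed scale also does not weight equal gaps equally: at powers 3.2 to 5.7, 85 versus 90 counts 1.31 to 1.77 times as much as 75 versus 80. A back-transformed centre is not strictly a mean either. The documents do not say, however, that the groups will lie in such different regions, and the simulated gaps differ from the raw ones by a fraction of a point.

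The alternatives bring no clear gain. A rank test performed no better than Box-Cox. Keeping the original scale whatever the normality test shows, with bootstrap or robust intervals, makes the estimate simpler to read. In the skewed case it also gives up power, because the untransformed F test lost 0.943 − 0.885 = 0.058, about 6 points, against Box-Cox. That is a fair trade-off, not a correction. Zeros in latency or mood scores are conditional and secondary, and standard software refuses such data, so the problem would be noticed.

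**Conclusion.** The concern is right about the word and wrong about the consequence. Box-Cox is mislabelled, but the method named is a recognised remedy for skewed data. A competent analyst would choose the power by likelihood, apply it consistently, and report sleep efficiency back-transformed in percentage points. Followed that way, the plan showed Type I error of 0.043 to 0.055, power at or above that of the rank test, and a recovered gap within about 0.1 point of the raw one on average. The apparent 70,000-fold instability shrinks to 1.08-fold once the units are standardised.

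This rests on assumed capped shapes with SD 6.9, since the documents give none. It also rests on one value per person, whereas the study plans 10 days of actigraphy and a mixed model; the direction of any resulting error is unknown. The finding that the word is wrong needs none of these assumptions. The point is a clerical slip with a gap that is filled sensibly in practice, and no change to the plan is needed.
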